8.2.2. Visit 2: Randomisation and IMP infusion

- Randomisation will be performed as soon as possible after inclusion and after the start of prostaglandins infusion (see Section 8.1.3).
- IMP administration
 - A third party reconstitutes the IMP (see [Section 6.4.2](#)).
 - The start of IMP infusion corresponds to H0 and should be within the 30 minutes following the start of prostaglandins infusion.
 - The start and the end times and the administered volume will be collected in the CRF.
- Concomitant treatments including intravenous fluids and blood products;
- Local tolerance which occurred during IMP infusion and AEs if any.

8.2.3. Visit 3: H2 (120 ± 30 min) / Blood sampling 2

The following data will be collected in the CRF:

- Blood sampling:
 - Complete blood count, Hb, Ht, platelets,
 - Haemostatic profile: fibrinogen, PT, QT, aPTT, D-dimers,
- Vital signs
 - Measurement of arterial blood pressure (systolic and diastolic),
 - Heart rate;
- Haemorrhage parameters:
 - Measured or estimated volume of blood loss from the start of bleeding;
- Concomitant treatments including intravenous fluids, blood products, tranexamic acid and fibrinogen concentrate as rescue therapy: any modification or institution of a new treatment;
- AEs if any.

8.2.4. Visit 4: H6 (360 ± 30 mn) / Blood sampling 3

[figure not shown]
The following data will be collected in the CRF:

- Blood sampling:
 - Complete blood count, Hb, Ht, platelets,
 - Haemostatic profile: fibrinogen, PT, QT, aPTT, D-dimers,
- Vital signs
 - Measurement of arterial blood pressure (systolic and diastolic);
 - Heart rate;
- Haemorrhage parameters:
 - Measured or estimated volume of blood loss from the start of bleeding;
- Concomitant treatments including intravenous fluids, blood products, tranexamic acid and fibrinogen concentrate as rescue therapy: any modification or institution of a new treatment;
- AEs if any.

8.2.5. Visit 5: morning of D2 / Blood sampling 4

Depending on the time of delivery, the assessment in the morning of D2 may differ from H48 (considering that the first blood sampling in hospital is performed around 7h00 in the morning).

H0 = start of IMP administration

Even if the patient has been transferred to another hospital or department within the same hospital, the investigator must ensure that all laboratory analyses will be performed, and the following parameters will be recorded in the CRF:

- Blood sampling:
 - Complete blood count, Hb, Ht, platelets,

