8.3. Assessments

1) Clinical assessments

Clinical assessment	Time of assessment
Physical examination: It will include a comprehensive standard evaluation of all systems, like: cardiovascular system, respiratory system, skin and appendices, gastrointestinal system, ear-nose-throat, lymphatic nodes, spleen, central nervous system, eyes, musculoskeletal system, endocrine system, argental system, psychiatric state. Signs for possible thrombosis will be checked.	Inclusion Discharge of the hospital
Vital signs (arterial blood pressure and heart rate)	Inclusion H2, H6 Morning of D2 Hospital discharge
Maximum SOFA score	Upon discharge of resuscitation and/or intensive care and/or PICU and/or continuous care units (if any)

2) Laboratory assessments

Plasmatic assessments	Volume of blood sample	Type of tube	Time of assessment
Complete blood count, platelets, Hb, Ht	10 ml	EDTA	Inclusion, H2, H6 and D2
Fibrinogen, PT, QT, aPTT, D-dimers	5 ml	Sodium citrate	
Creatinine	5 ml	EDTA	Inclusion and D2

Urea	4 ml	Lithium heparinate	
------	------	--------------------	--

A total of 78 mL of blood will be collected throughout the study according to the protocol. All biological parameters will be determined locally.

Any abnormal laboratory finding judged clinically significant by the investigator will be considered as an adverse event.

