9.2.1. Known and potential risk(s) related to the IMPs

- Clottafact®

As specified in the Risk Management Plan of Clottafact®, the potential risks are:

Thromboembolic events:

Venous and arterial thromboembolic events are the main safety concerns associated with the use of fibrinogen concentrate. However, several minimisation actions are taken in order to limit the potential risks, which are detailed thereafter (see [Section 9.3](#)).

Anaphylactic reactions:

Immunoallergic events and anaphylactic accidents are potential concerns, which will be minimised by patient monitoring during administration.

Immunogenicity:

The occurrence of antibodies against fibrinogen is a very rare complication of fibrinogen replacement therapy. The risk of antifibrinogen antibodies appearance has been described only once in a patient with congenital afibrinogenaemia and rheumatic valvular heart disease.

Viral safety:

Clottafact® is purified from human blood of selected donors and its manufacturing process includes three viral/non-conventional transmissible agents removal/inactivation steps (solvent-detergent, dry heating and 35 nm filtration). Despite these highly secured procedures, the risk of viral infection or non-conventional transmissible agents cannot be totally ruled out.

Standard measures to prevent infections resulting from the use of medicinal products prepared from human blood or plasma include: selection of donors, screening of individual donations and plasma pools for specific markers of infection and the inclusion of effective manufacturing steps for the inactivation/removal of viruses. Despite these safety procedures, when medicinal products prepared from human blood or plasma are administered, the possibility of transmitting infectious agents cannot be totally excluded. This is also applied to unknown or emerging viruses and other pathogens. The previously mentioned measures are considered to be effective against enveloped viruses such as HIV, HBV, HCV and for the non-enveloped viruses HAV and parvovirus B19. There is reassuring clinical experience regarding the lack of hepatitis A or parvovirus B19 transmission and it is also assumed that the antibody content makes an important contribution to the viral safety.

- Placebo

At the planned conditions of use of Clottafact[®] placebo, no risk is expected.

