9.5.3. Definition of Specific Events in the Study

All PPH including their time course and progression will be appropriately documented on the case report form as part of the efficacy parameters as well as all transfused units and/or procedures required to manage and treat them. They will not be reported as AEs/SAEs.

Patients who suffered from PPH may develop signs and symptoms related directly to that bleeding such as anaemia, thrombocytopenia, hypofibrinogenemia, worsening of haemorrhage. PPH may also lead to occurrence of morbidity (corresponding to any haemostatic intervention: uterine ligation, embolization, intrauterine balloon, vascular ligation, hysterectomy) being considered as disease-

related. All these signs, symptoms and procedures will not be reported as adverse events or as serious adverse events.

Although they may be emergent when treated with IMP, the investigator has to describe them as part of the bleeding (efficacy parameters) and not as AEs/SAEs if they are directly and unequivocally related to the bleeding.

In this trial, the following adverse events should always be considered and reported as serious adverse events:

- Any deep venous or arterial thromboembolic event, whatever the causality assessment.
- Any suspicion of infectious agents transmission by the IMP.

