10.2. Assessment of Safety

AEs and SAEs from all patients followed throughout the study will be recorded and reported, as described in [Section 9.5](#), whether or not the AE was determined to be related to the administration of IMP.

Safety evaluation will include the monitoring of the following items:

- Physical examination performed at inclusion and hospital discharge;
- Vital signs (blood pressure and heart rate) will be monitored at inclusion visit, randomisation, H2, H6, discharge from the obstetrics room, morning of D2, intensive care unit discharge (if applicable) and hospital discharge.
- Tolerance of fibrinogen concentrate administration
 - Serious and non-serious adverse events (AE)
 - Symptomatic thromboembolic events within the 6 weeks following the administration of IMP.

In this study, all events related to PPH (anaemia, progressing or worsening of haemorrhage) will not be reported as AEs as they are already reported as efficacy criteria.

- Laboratory parameters:
 - Change in creatinine and urea between inclusion and D2
 - Change in TP, aPTT, D-dimers, platelets between inclusion and each determination times.

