1.3 Flow chart

An outline of the study procedures is presented in the table below.

Table 1 Study flow-chart

	CONSENT FORM	INCLUSION	TREATMENT	FOLLOW-UP				END OF STUDY
	Visit 1 Inclusion Blood sampling 1	Visit 2 Randomisation IMP infusion	Visit 3 Blood sampling 2	Visit 4 Blood sampling 3	Visit 5 Morning of D2 Blood sampling 4	Visit 6 Hospital discharge	Visit 7	
	Before H0	H0 = start of IMP infusion*	H2 (120 ± 30 min)	H6 (360 ± 30 min)			6 ± 2 weeks after delivery	
Informed consent	x							
Inclusion/exclusion criteria	x	x						
Demographics		x						
Medical history (including thromboembolic and obstetrical events and any clinically relevant medical condition)		x						
Pregnancy parameters		x						
Delivery parameters		x						
Clinical exams								
PPH parameters		x	x	x	x		x	
Physical examination		x					x	
Vital signs (arterial pressure, heart rate)		x		x	x	x	x	
Stay in ICU data (if applicable)								
SOFA score maximum**							x**	
Laboratory tests								
Biochemical tests (plasmatic creatinine and urea)		x				x		
Coagulation tests (fibrinogen, PT, QT, aPTT, D-dimers)		x		x	x	x		
Haematological tests (CBC, Hb, Ht, Plt)		x		x	x	x		
Treatments								

December 20th, 2018, Final2.0

 <small>Fibrinogen in haemorrhage of DELivery</small>	CONSENT FORM	INCLUSION	TREATMENT	FOLLOW-UP				END OF STUDY
		Visit 1	Visit 2	Visit 3	Visit 4	Visit 5	Visit 6	Visit 7
Prior treatments		x						
Concomitant treatments		x	x	x	x	x	x	x
Resuscitation fluids		x	x	x	x	x		
Transfusions of blood products		x	x	x	x	x	x	x
IMP								
Reconstitution			By a third party					
Administration			H0*					
Adverse event collection			x	x	x	x	x	x

* Start of IMP infusion should be within the 30 min following the start of prostaglandin infusion and at a flow rate ≤ 20 ml/min

** SOFA score will be assessed only for patients transferred in an Intensive Care Unit

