4.4 Vital signs

Vital sign parameters will be described at inclusion visit, H2, H6, discharge from the obstetrics room, D2, intensive care unit discharge (if applicable) and hospital discharge :

- Systolic blood pressure (mmHg) at each visit and minimal value since last visit
- Diastolic blood pressure (mmHg) at each visit and minimal value since last visit
- Heart rate (beats/min) at each visit and minimal value since last visit

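### No blood pressure or heart rate is scheduled between the start of infusion and H2, the between-visit heart-rate summary is a minimum, and the plan carries three different vital-sign schedules

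*Protocol*

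**What the plan says.** Protocol 10.2 sets the safety schedule: "Vital signs (blood pressure and heart rate) will be monitored at inclusion visit, randomisation, H2, H6, discharge from the obstetrics room". It then adds the morning of D2, intensive care discharge where applicable, and hospital discharge.

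The flow charts in the protocol synopsis and SAP 1.3, the visit descriptions in Protocol 8.2 and the table in Protocol 8.3 give a shorter schedule: inclusion, H2, H6, morning of D2 and hospital discharge. Visit 2, at which the product is infused, has no vital-sign entry in any of them. What Protocol 8.2.2 does collect there includes "Local tolerance which occurred during IMP infusion and AEs if any", along with infusion times, volume and concomitant treatments.

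SAP 4.4 gives a third list: "Vital sign parameters will be described at inclusion visit, H2, H6, discharge from the obstetrics room, D2, intensive care unit discharge", and hospital discharge. It also plans a between-visit extreme for systolic pressure, diastolic pressure and heart rate. For heart rate it reads "Heart rate (beats/min) at each visit and minimal value since last visit"; the two pressures are treated in the same way.

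Protocol 9.2.1 names anaphylactic reactions as a potential risk, "which will be minimised by patient monitoring during administration". Protocol 9.3 relies on regular vital-sign assessment to detect adverse events early. Neither section gives measurements or times.

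**The concern.** The infusion is when an acute reaction to a plasma-derived product is most likely to be sought, and the protocol itself names monitoring at that time as its safeguard. Yet no schedule turns that safeguard into a recorded, timed blood pressure or heart rate.

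The between-visit value in SAP 4.4 only partly makes up for this. It carries no time, so it cannot place a change before, during or after the infusion. For blood pressure a minimum is at least the useful extreme. For heart rate it is the wrong end of the range: in haemorrhage or an infusion reaction the sign of interest is a rise. SAP 3.3.6.1.2 itself uses a threshold of 100 beats/min or more.

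At stake is how well the safety tables can describe the period around the infusion in each arm. The disagreement between the schedules is a second, smaller matter. SAP 4.4 plans rows for obstetrics-room and intensive care discharge that the visit schedule never asks sites to record.

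**Working it through.** The plan states no figure to reproduce here. The check is a count of time points and a calculation of the interval without a scheduled reading.

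**1. Schedules side by side**

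| Time point | Protocol 10.2 | Both flow charts, Protocol 8.2 and 8.3 | SAP 4.4 |
|---|---|---|---|
| Inclusion | yes | yes | yes |
| Randomisation | yes | no | no |
| H2 | yes | yes | yes |
| H6 | yes | yes | yes |
| Obstetrics-room discharge | yes | no | yes |
| Morning of D2 | yes | yes | yes |
| Intensive care discharge | yes | no | yes |
| Hospital discharge | yes | yes | yes |
| **Total** | **8** | **5** | **7** |

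Protocol 10.2 exceeds the visit schedule by three points: randomisation, obstetrics-room discharge and intensive care discharge. It exceeds SAP 4.4 by one, randomisation.

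**2. Where the randomisation reading falls.** Protocol 8.1.3 defines randomisation as assigning the treatment unit. That comes before reconstitution and so before H0, which Protocol 8.2.2 defines as the start of infusion. The reading is therefore pre-infusion. Scheduled readings after H0 and before H2: 0 in every list.

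**3. Length of the gap**
- H2 window (Protocol 8.2.3): 120 ± 30 min, so 90 to 150 min after H0.
- Volume 200 mL, flow rate at most 20 mL/min (Protocol 6.4.2). Shortest infusion: 200 / 20 = 10 min.
- First scheduled reading after the earliest possible end of infusion: 90 − 10 = 80 min to 150 − 10 = 140 min.

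The 80 to 140 minutes is the longest case. A slower infusion ends later and shortens the gap after it. The 90 to 150 minutes from H0 does not depend on the flow rate.

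**4. What the between-visit summary can show.** SAP 4.4 plans three minima (systolic, diastolic, heart rate) and no maxima. The lowest heart rate in an interval reaches 100 only if every contributing value is 100 or more. A rise that begins and settles within the interval leaves the minimum unchanged. Tachycardia that persists to a visit appears in the value recorded at that visit, which SAP 4.4 also plans to describe. What is lost is the transient rise between visits, including one between H0 and H2.

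**The case against.** The best reply is that patients are watched during the infusion and events are captured. Much of that stands. Visit 2 collects local tolerance and adverse events, Protocol 9.4 requires the infusion to be stopped for an allergic reaction, and SAP 6.5 classifies adverse events by their start time against H0. The monitoring in Protocol 9.2.1 can be read as a commitment to bedside care, not to a data table. A recognised anaphylactic reaction would be a reportable event.

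Three stronger readings are tempting, and the documents do not support them.

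- *The infusion is unobserved, or reactions would go unreported.* Visit 2 collection contradicts this. Protocol 9.5.3 does exclude some findings: "All these signs, symptoms and procedures will not be reported as adverse events or as serious adverse events". But the exclusion applies only to findings directly and unequivocally due to the bleeding, and its examples include neither tachycardia nor allergic reactions. A heart-rate change escapes both the SAP 4.4 summaries and the adverse-event tables only if it is transient, settles before H2, and is either attributed to bleeding or not recognised as an event.
- *The planned summaries cannot show tachycardia at all.* Sustained tachycardia appears in the per-visit values.
- *The covariate of heart rate 100 or more in SAP 3.3.6.1.2 is derived from the minimum and would distort the imputation analysis.* Nothing links the two. The per-visit readings are an equally available source.

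A further objection is that a protocol change comes too late: recruitment closed on 30 June 2018 with 448 patients (SAP 1.11). That stands, and limits what can be changed for this trial to the SAP.

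**Conclusion.** The point holds in a limited form. No schedule places a recorded blood pressure or heart rate between H0 and H2, a gap of 90 to 150 minutes from the start of infusion. The three schedules list 8, 5 and 7 points. The between-visit heart-rate summary uses the extreme that misses a transient rise.

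The effect is confined to descriptive safety data. SAP 4.4 plans no test on vital signs, and nothing shows that the primary or secondary efficacy analyses depend on these summaries. The blood-pressure minimum can still show a lower pressure in one arm, without timing it to the infusion. This is a modest improvement to make, not a flaw that threatens the trial's conclusions.

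The CRF is not among the documents. Whether it holds a maximum heart rate, or readings at the points found only in Protocol 10.2 and SAP 4.4, is unknown, and the fix allows for either case.

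**What to change.** **SAP 4.4, before unblinding**
- Keep the minimum since the last visit for systolic and diastolic pressure.
- For heart rate, summarise the maximum since the last visit if the CRF collected it. If not, report the highest recorded value after H0 and state that it cannot recover a rise between H0 and H2.
- Limit the rows to the time points actually collected.

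This takes one changed summary statistic, one sentence if the fallback is used, and a check of the rows. It needs no new data.

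**Protocol design (for a later trial; too late for the patients enrolled here)**
- Keep the pre-infusion reading already in Protocol 10.2 and add one blood-pressure and heart-rate reading at the end of infusion to Visit 2.
- Use one list in both flow charts, Protocol 8.2, 8.3 and 10.2, and SAP 4.4: inclusion, before H0, end of infusion, H2, H6, obstetrics-room discharge, D2, intensive care discharge if applicable, and hospital discharge. That is 8 + 1 = 9 points.

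Counted against the list in Protocol 10.2, the cost is one bedside reading and its CRF fields per patient.

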11. DATA MANAGEMENT

11.1. CRF completion guidelines

11.1.1. Introduction

All of the information required to be reported to the Sponsor as per protocol will be entered in the printed Case Report Forms (CRFs) for each study patient. The CRFs must be completed by the Investigator or any study centre staff designated by the Investigator.

The Investigator is responsible for ensuring that data recorded in the CRFs are complete, accurate and legible. The CRFs should be completed as soon as possible after the patient's visit and before review by the Monitor at the latest.

11.1.2. General instructions

11.1.2. 1. Overview

The CRFs are printed on NCR paper (triplicate). CRFs should be completed in English with a black ballpoint pen.

All data in the CRFs must come from and be consistent with the source documents, i.e. patient's file or medical records.

Any discrepancy between the data in the CRF and those in the source documents should be documented by the Investigator.

No data field will be left blank.

Abbreviations will be avoided since they are often ambiguous.

No data should be written in the margins.

11.1.2. 2.Header information

Header information should include at least:

- The protocol number,
- The name of the visit,
- Patient's identification:
 - a) Initials by default: the first letter of the last name (surname) and the first letter of the first name (name) are recorded. Example: Robert Smith: | S |-| R
 - b) Patient identification number according to local requirements: patient number is recorded with the centre number provided by the Monitor at the set-up visit. The patient number is a sequential number incremented with each patient included in the order of signature of informed consent. Example: 3rd patient included in the centre number 10 : | 1 | 0 |-| 0 | 3 |

11.1.2. 3.Recording dates and time

Dates will be recorded in the CRF using two digits for the day and the month and four digits for the year.

- Example: February 28, 2005 must be entered as 28/02/2005.

Time will be recorded using four digits according to the 24-hour clock.

- Example: 3:25 pm must be entered as 15:25.

11.1.2. 4.Recording of missing data

Before the Monitor reviews the data during the monitoring visits, the Investigator should make every effort to provide the information required. Use of the following codes should be kept to a minimum.

The Investigator should enter in the CRF:

- If the requested item is unknown or not available: UNK.
- If the requested item is not applicable: NA
- If the requested item was not done: ND

11.1.2. 5. CRF corrections

If the Investigator makes an error, he/she should cross out the data item, clearly enter the new data item and initial and date the correction. The use of opaque white correction fluid is prohibited. The corrections should be made while the NCR copies are still together on site.

11.1.2. 6. Confidentiality

Patient names must be kept confidential and should not appear on any CRF page or study-specific documents.

11.1.2. 7. CRF Completion in case of screening failure or premature withdrawal

A CRF must be completed for all patients with a signed informed consent up. Screening failure and premature withdrawal must be documented on the end of study form of the CRF with the cause that has led to screening failure/premature withdrawal.

11.1.3. Collection of CRF

The CRF will be checked by the Monitor during monitoring visits.

After the required corrections have been done by the investigator, the Monitor will collect two copies of each page of the CRF (the original which will be sent to the data manager and one copy which will be kept by the Monitor). The third copy will be archived by the Investigator.

The frequency of monitoring visits will depend on the recruitment rate of each centre.

11.1.4. Specific Case Report Form instructions

Specific instructions for completing the case report form will be detailed in a specific document “CRF completion guidelines”.

11.2. CRF and Data Handling

Data processing, from data collection to database lock, will be carried out in accordance with GCP (see ICH-E6, Section 5).

The data handling documents, e.g. annotated CRF, database structure, data entry manual, coding rules and computerised validation, are defined in a Data Management Plan.

The database and data entry screens will be created in a software specifically designed for clinical data management, in compliance with ICH-E6 requirements.

All CRFs received in the Data Management Unit will be tracked and reviewed by the Data Manager before double data entry. The consistency of data will be checked by computerised programs and related queries will be generated for resolution by the Investigator. The database will then be updated accordingly.

Medical terms and drug names will be coded. Quality controls will be made to ensure the overall quality and consistency of the database. Reconciliation of SAE reports with the pharmacovigilance database will also be carried out.

At the end of the data handling process, a data review meeting will be held in order to prepare the database lock. After database lock, data will be transferred into SAS and STDM CDISC file formats for performing statistical analyses.

